### 9.1. Definitions

- Disease control rate: please see Study Endpoints (section 2) above
- Maximal PSA change: Best PSA response divided by baseline PSA x 100%]
- Best PSA response: Baseline PSA minus lowest on-study PSA at any time
- PSA doubling time (PSADT): calculated as per the PCWG3 and Memorial Sloan Kettering Cancer Center calculator ([https://www.mskcc.org/nomograms/prostate/psa\\_doubling\\_time](https://www.mskcc.org/nomograms/prostate/psa_doubling_time)) with linear regression model of natural logarithm of PSA and time, based on:
  - At least 3 consecutive PSA values with each value  $\geq 0.2$  ng/mL
  - Interval between first and last PSA values is  $\geq 8$  weeks but  $\leq 12$  months

PSADT should be calculated based on pre-study PSAs and based on the last 3 PSAs prior to EOT. If subject comes off trial prior to cycle 4, then EOT PSADT cannot be calculated since the first of three values would coincide with baseline value at cycle 1 day 1.

- Radiographic progression to metastatic disease:
  - Lymph nodes must have grown by at least 5 mm in the short axis from baseline or nadir and be  $\geq 1.0$  cm in short axis to be considered to have progressed. If the node progresses to  $\geq 1.5$  cm in the short axis, it is considered pathologic (metastatic) in the absence of alternative explanation. Nodes that have progressed to between 1.0 and less than 1.5 cm are subject to clinical discretion.
  - New unequivocal visceral lesions are determined by RECIST 1.1 criteria
  - Bone metastases are difficult to assess. PCWG3 recommends recording the date of unequivocal development of new sites on bone scintigraphy, then continuing therapy (assuming it is well tolerated and there is no clinical reason to discontinue it) until two additional new lesions are detected. If two new lesions are subsequently detected, these must be confirmed at the time of next bone scan; if confirmed, date of progression is the date these two new lesions were initially detected. **All cases of progression called on bone scan must be reviewed by the overall PI to confirm adherence to PCWG3 guidelines.** Sites should ask interpreting radiologists to enumerate bone lesions for all such cases.

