## **5.2. Nivolumab Administration**

Nivolumab will be given on day 1 of a 28-day cycle at a dose of 480 mg intravenously (IV). All visits have a window of +/- 3 days (see Study Calendar, section 7).

The administration of nivolumab infusion must be completed within 24 hours of preparation. If not used immediately, the infusion solution may be stored under refrigeration conditions (2°C to 8°C, 36°F to 46°F) for up to 24 hours, and a maximum of 8 hours of the total 24 hours can be at room temperature (20°C to 25°C, 68°F to 77°F) and room light. The maximum of 8 hours under room temperature and room light conditions includes the product administration period. The unopened vials can be stored at room temperature (up to 25°C, 77°F) and room light for up to 48 hours.

Nivolumab injection is to be administered as an IV infusion over 30 minutes (acceptable window is 25 minutes to 40 minutes) through a 0.2-micron to 1.2-micron pore size, low-protein binding (polyethersulfone membrane) in-line filter at the protocol-specified doses

and infusion times. It is not to be administered as an IV push or bolus injection. Nivolumab can be infused undiluted or diluted so as not to exceed a total infusion volume of 160 mL. For patients weighing less than 40 kilograms (kg), the total volume of infusion must not exceed 4 mL per kg of patient weight.

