## 7. STUDY CALENDAR & EVALUATIONS

Event	Screening	On Treatment (28-day cycles)	End of Study i	Follow-Up
	≤ 28 days prior to enrollment	Day 1 j	Within 30 days of last dose	Every 3 months until mPCa
Informed consent	X			
Confirmation of all eligibility criteria	X k			
Medical history a	X		X	X l
Prior systemic and radiation therapy b	X			
Physical examination c	X	X	X	
ECOG performance status	X	X	X	
Concomitant medication review	X	X	X	
Adverse Event review	X	X	X	X l (100 days after last nivolumab dose)
Chemistries d	X	X		
Hematology d	X	X		
TSH (with reflex free T4 testing if abnormal)	X	X		
Prostate-specific antigen e	X	X	X	
Archival tissue testing for PD-L1 expression and NGS f	X (After tissue pre-screen consent, prior to full informed consent, for patients enrolled under AM2)			
Blood for exploratory studies g		Cycles 1 and 2; q4 cycles beyond cycle 4 (C5, C9, etc.). Optional collection 1 week after cycle 1.	X	
Radionuclide bone scan and CT of abdomen/pelvis with contrast h	X	X (Prior to cycle 4 and every 3 rd cycle thereafter)		
Nivolumab administration		X		

Abbreviations: AE=adverse event; CBC=complete blood count; ECOG=Eastern Cooperative Oncology Group (performance score); EOS=end-of-study; mPca=diagnosis of metastatic prostate cancer; NGS=next-generation sequencing (e.g. Foundation One, OncoPanel).

- a Medical history: including relevant medical history collection, as well as Gleason score and TNM stage at diagnosis, results of any recent advanced imaging (Axumin, SPECT, choline, sodium fluoride, etc.)
- b Collect radiation site, administered dose per fraction and treatment duration, as well as any concurrent ADT and duration of ADT.
- c Physical examination includes height (at screening only), weight, vital signs, and general physical examination

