#### **12.2.2. Secondary analysis and analysis of safety**

Maximum PSA change and best PSA response will be summarized descriptively and graphically in waterfall plots. PSA doubling time will be calculated with linear regression model of natural logarithm of PSA and time. PSADT at baseline and

EOS will be summarized, and change in PSADT, as captured by the change in PSA slope, will be summarized descriptively as well. Time to event endpoints will be summarized using Kaplan Meier estimate.

All reported toxicities, regardless of attribution, will be summarized by toxicity type and maximum grade. The maximum grade consolidates the reports of a given toxicity for a patient over time by taking the maximum across time. Immune modulatory medication used for toxicities will also be summarized descriptively.

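### On-treatment PSADT uses only the last three PSAs, under rules that can exclude visit-compliant men, early stoppers and some deep responders

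*Combined protocol and SAP*

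**What the plan says.** Change in PSADT from baseline is a secondary endpoint (section 2.2.2). Section 9.1 defines PSADT by two conditions: "At least 3 consecutive PSA values with each value" at or above 0.2 ng/mL, and "Interval between first and last PSA values is" no less than 8 weeks and no more than 12 months. It then states: "PSADT should be calculated based on pre-study PSAs and based on the last 3 PSAs prior to EOT". It adds: "If subject comes off trial prior to cycle 4, then EOT PSADT cannot be calculated". The reason given is that the first of the three values would be the cycle 1 day 1 baseline.

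On analysis, section 12.2.2 says "PSA doubling time will be calculated with linear regression model of natural logarithm of PSA and time". It reports the change as a change in slope, descriptively and without a test.

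On timing, section 5.2 says "Nivolumab will be given on day 1 of a 28-day cycle" and "All visits have a window of +/- 3 days". The study calendar (section 7) schedules a PSA on day 1 of each cycle and another at the end-of-study visit, timed "Within 30 days of last dose".

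No section says what happens when a span falls short of 8 weeks or an on-treatment value is below 0.2 ng/mL. The time point is EOT in 9.1, end-of-study in 2.2.2 and EOS in 12.2.2.

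**The concern.** The conditions in 9.1 suit the selection of patients with a measurable rise. Applied on treatment, they decide who contributes to the endpoint, and partly by outcome. Men who stop early are unlikely to be a random subset, and the cycle-4 rule removes all of them. The 0.2 floor can remove a man because his PSA fell. The 8-week minimum equals the nominal length of three visits, so a visit a day or two off schedule, within the window, can remove a compliant man.

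With at most 34 patients in two cohorts of 20 and 14, losing several from a descriptive summary matters. The discarded cycle 1 to cycle 4 values would also have made the slope more precise.

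**Working it through.** **The plan's own figure.** Section 2.2.1 gives 7.18% monthly growth and a 23% rise over 3 months at a 10-month doubling time. Check: 2^(1/10) − 1 = 7.18%, and 1.0718^3 − 1 = 23.1%. The figure reproduces. The matching log-PSA slope is ln 2 / 10 = 0.069 per month. The documents give no figure for how many men will have a calculable on-treatment PSADT.

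**Span.** Inputs: 28-day cycles and a window of 3 days either side (5.2), 8-week minimum (9.1).
- Cycle 2, 3 and 4 day 1 are days 29, 57 and 85. Nominal span: 85 − 29 = 56 days, exactly 8 weeks.
- Window limits: 56 − 6 = 50 to 56 + 6 = 62 days.
- Let p be the chance that a visit is on its due day, with the rest spread evenly over the other six days and visits independent (an assumption). The span fails when the last visit deviates earlier than the first, so P(fail) = [1 − p² − 6((1 − p)/6)²] / 2.

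| Share of visits on the due day | P(span under 56 days) |
|---|---|
| 100% | 0% |
| 90% | 9% |
| 70% | 25% |
| 50% | 35% |
| 1/7 (uniform) | 21/49 = 43% |

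If all men were otherwise calculable, 43% would be 14.6 of 34 (8.6 of 20 and 6.0 of 14).

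If the end-of-study PSA counts as the third value (cycle visits uniform over their windows), the shortfall is 89% with that visit uniform on days 1–30 after the last dose, 68% on days 21–30 and 31% on days 28–30.

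**Cycle-4 exclusion.** Its stated reason assumes that the end-of-study PSA does not count. If it does, a man whose last dose is cycle 3 has cycle 2, cycle 3 and end-of-study values without using cycle 1. With cycle visits on their due days, his span can reach 28 + 30 = 58 days.

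**Floor.** Fall needed to drop below 0.2 ng/mL = 1 − 0.2/baseline: 60% from 0.5 (the lowest eligible PSA, section 3.1), 80% from 1, 90% from 2, 96% from 5 and 98% from 10 ng/mL. The baseline PSA distribution is not given, so the share lost cannot be computed.

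**Precision.** SE(slope) = σ / √Σ(t − t̄)².
- Three points at 0, 28, 56 days: sum of squares 2 × 28² = 1568, root 39.6.
- Four points at 0, 28, 56, 84 days (cycle 1 to cycle 4 day 1): 2 × 42² + 2 × 14² = 3920, root 62.6.
- Ratio 39.6 / 62.6 = 0.63, so the SE is 37% smaller at any CV.
- The documents give no PSA CV. Assuming 5%, 10% and 15%, the three-point SE is 0.038, 0.077 and 0.115 per month, against the 0.069 slope above.

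**Baseline slope.** Entry requires PSADT under 10 months, so the observed pre-study slope is selected. A simulation with no treatment effect (400,000 men per setting, three pre-study values, lognormal true PSADT with log-SD 0.5) gave this change in mean slope at CV 10% and a true median of 10 months: −36% with an 8-week pre-study span, −9% with 6 months, −3% with 12 months. Over CV 5–15%, medians of 6 and 10 months and those three spans, the fall ranged from 0.1% to 48%.

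**The case against.** The strongest reply is that this is one untested, descriptive endpoint in an exploratory single-arm trial, that deep responses are shown elsewhere (maximal change and best response, in waterfall plots), and that barring cycle 1 day 1 is a reasoned choice because it is the baseline. The first two parts stand and limit the weight of the point. The third is a choice, not a mathematical limit: a slope can start at its origin.

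Several stronger readings are tempting, and the documents do not support them.
- *The best responders are dropped.* Only those who fall below 0.2 ng/mL are. Men with higher baselines stay in after deep falls. After primary radiation, entry PSA is at least 2 ng/mL above nadir, so the fall must exceed 90%. A falling PSA is not itself excluded, because 12.2.2 works on the slope.
- *43% of on-schedule men are lost.* That needs uniform use of the window, for which the documents give no evidence.
- *The three-point slope is too noisy to use.* That depends on an assumed CV; at 5% the SE is well below the slope.
- *The last three values always capture a rise that led to stopping.* Section 6.7 has no mandatory PSA stopping rule and lists many other reasons to stop. Where a PSA-driven stop does occur, it works against regression to the mean, so the net direction of bias is not known.
- *This calculation drives continued treatment.* The synopsis and 6.7 mention PSADT only as an example within investigator judgement during treatment. The 9.1 figure is computed at the end.

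One further objection bears on the remedy. Section 6.7 notes that a PSA benefit may take 12 weeks or more to appear, so a single slope from cycle 1 day 1, or a model with a knot there, could dilute a late effect. That stands, and is why the last-three version should be kept alongside.

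**Conclusion.** The concern holds in this form. As written, 9.1 removes every man off before cycle 4, can remove visit-compliant men through a minimum span with no slack, and removes deep responders with a low baseline. The change in PSADT is then summarised in a subset that depends partly on outcome, with less precision than the scheduled PSAs allow.

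The cycle-4 exclusion and the 50-to-62-day range follow from the text. The loss through the window is 0% to 43% for day-1 visits, depending on visit adherence, which the documents do not give. The 37% gain in precision holds at any CV. Regression to the mean may produce some apparent lengthening of PSADT, from near zero to large, depending on pre-study span, PSA variability and the true PSADT distribution, none of which is given. It is a caution for interpretation, not a demonstrated bias of known size.

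The sponsor should make the change. The primary endpoint, sample size and decision rules do not depend on it.

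**What to change.** In 9.1 and 12.2.2:
1. Estimate each man's on-treatment log-PSA slope from all scheduled PSAs from cycle 1 day 1 to the end-of-study visit or start of ADT. Drop the 8-week minimum and the cycle-4 exclusion for these values.
2. Keep values below 0.2 ng/mL, treating undetectable results as left-censored at the assay limit.
3. Report the change in slope with a confidence interval and the number of men contributing.
4. Keep the last-three PSADT as a sensitivity analysis, which also covers a delayed effect.
5. Use one term for EOT and EOS, reconcile the minimum of three values with the last-three rule, and state whether the end-of-study PSA counts.
6. State in the interpretation that the pre-study slope was selected for PSADT under 10 months, so part of any lengthening may be regression to the mean. Using more on-treatment values does not remove this.

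The cost is a change of wording and a little extra analysis; the on-treatment PSAs are already scheduled. The drawbacks are that one slope averages over any delayed effect and that slopes from very few values will be imprecise.

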	
nivolumab. PD-L1 tumor-cell expression on primary tissue samples (prostatectomy or diagnostic core biopsies) will be prospectively assessed and used to assign subjects to one of two groups (positive vs. negative). Next-generation sequencing will also be performed upon enrollment but will be used only for exploratory studies. If subjects experience PSA stabilization (<10% increase from baseline) or responses, they will continue nivolumab for up to 2 years in the absence of progression to metastatic disease or unacceptable toxicity. Patients who have stabilization of PSA in the absence of radiographic or clinical progression may also continue treatment. Patients who have isolated PSA progression at 12 weeks can be continued on treatment by investigator's discretion if they are believed to be clinically benefitting (for example, if they experience decreased PSA doubling time) and have not demonstrated symptomatic or radiographic evidence of metastatic disease.

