### **2.1.2. Secondary Objectives**

- Determine the maximal change (proportional) and best decline (absolute) in prostate specific antigen (PSA) during nivolumab treatment
- Describe the change in PSA doubling time (PSADT) during nivolumab therapy relative to baseline
- Determine the time to development of overt metastatic disease after treatment with nivolumab
- Determine the time to initiation of androgen deprivation therapy (ADT) after treatment with nivolumab
- Assess the toxicity of nivolumab monotherapy in patients with BCR PCa

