### **2.2.2. Secondary Endpoints**

- Maximal change in prostate specific antigen (PSA) during nivolumab treatment, as a percentage of baseline
- Best PSA response during nivolumab treatment, as an absolute change relative to baseline
- Change in PSA doubling time (PSADT) at end-of-study relative to baseline
- Time from enrollment to PSA progression (10% or greater increase in PSA relative to baseline)
- Time from enrollment to development of radiographic metastatic disease
- Time from enrollment to initiation of ADT
- Safety of nivolumab

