## 6.7. Protocol Therapy Discontinuation

In addition to discontinuation from therapy related to toxicities as outlined above, a subject will also be discontinued from protocol therapy and followed per protocol under the following circumstances outlined below. The reason for discontinuation of protocol therapy will be documented on the electronic case report form (eCRF).

The Prostate Cancer Working Group 3 (PCWG3) recognizes that favorable effect of experimental therapies on PSA may be delayed for  $\geq 12$  weeks and recommends continuing treatment through early rises for a minimum of 12 weeks unless there is other evidence of progression.

PCWG3 recommends continuing experimental therapies for subjects who experience PSA rise after initial decline, in the absence of any radiographic or clinical progression. However, subjects in this trial do have access to a standard-of-care treatment in the form of ADT which can be used to delay development of metastatic disease, although a convincing survival benefit has not been established in this setting. This trial requires treatment discontinuation only for the reasons below, but investigators are advised to use discretion for patients with rapidly increasing PSAs (after 12 weeks of treatment). Patients believed to be clinically benefitting, for example based on decreased PSADT after starting nivolumab, could be continued on treatment at the investigator's discretion.

- Documented metastases on imaging (see Section 9 for definitions).
- Completed 2 years of treatment with nivolumab
- Site investigator determines a change of therapy (i.e. starting ADT) would be in the best interest of the subject
- Subject or legal representative (such as a parent or legal guardian) withdraws consent and requests to discontinue protocol therapy, whether due to unacceptable toxicity or for other reasons
  - In a subject decides to prematurely discontinue protocol therapy (“refuses treatment”), the subject should be asked if he or she may still be contacted for further

scheduled study assessments. The outcome of that discussion should be documented in both the medical records and in the eCRF.

- Unacceptable adverse experiences
- Intercurrent illness that prevents further administration of treatment
- Protocol therapy is interrupted for > 6 weeks (calculated from the date of the first missed dose). Any potential exceptions to this criteria must be discussed with and approved by the PI.

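### End-of-study PSADT is read in a window that the stop date sets, and stopping after week 12 may itself depend on PSADT; add a fixed C2–C4 slope beside it (optional improvement)

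*Combined protocol and SAP*

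**What the plan says.** Section 2.2.2 lists the secondary endpoint "Change in PSA doubling time (PSADT) at end-of-study relative to baseline". The matching objective in 2.1.2 is broader: "Describe the change in PSA doubling time (PSADT) during nivolumab therapy relative to baseline".

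Section 9.1 defines the measurement: "PSADT should be calculated based on pre-study PSAs and based on the last 3 PSAs prior to EOT". It adds "If subject comes off trial prior to cycle 4, then EOT PSADT cannot be calculated", on the ground that the first of the three values would then be the C1D1 baseline. Section 12.2.2 summarises PSADT at baseline and end of study, with the change expressed as a change in PSA slope, descriptively and without a test.

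On staying on treatment, the Synopsis says "Patients who have isolated PSA progression at 12 weeks can be continued on treatment by investigator's discretion if they are believed to be clinically benefitting", with PSADT as the example of benefit. Section 6.7 says "Patients believed to be clinically benefitting, for example based on decreased PSADT after starting nivolumab, could be continued on treatment at the investigator's discretion", and also advises discretion when PSA is rising fast after 12 weeks. Its list of reasons for discontinuation names neither PSA progression nor PSADT. It does include an investigator's judgement that a change of therapy, such as starting ADT, is best for the patient.

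The calendar in section 7 draws PSA on day 1 of each 28-day cycle and at an End of Study visit timed "Within 30 days of last dose".

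**The concern.** The on-treatment value is tied to each man's own stop date, and that date may depend on the quantity being measured. A man whose week 4–12 slope is steep by chance may be stopped, and that slope then becomes his final value. A man whose slope is flat by chance is more likely to continue, and his value is replaced by a later one. Upward noise is kept and downward noise is discarded, even when the drug does nothing.

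What is at stake is how one descriptive summary is read. With no drug effect it could suggest that PSA accelerated. With a real early effect it could hide part or all of it. The trial is meant to inform a larger one (section 1.9), and no fixed-time PSADT is planned against which a reader could check the result.

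**Working it through.** **Plan's own figure.** The documents give no figure for this endpoint. Section 2.2.1 supplies the growth model: a 10-month doubling time gives 2^(1/10) − 1 = 7.18% per month and 1.0718³ − 1 = 23% over 3 months. Both reproduce. The check uses the same log-linear growth.

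**Inputs from the documents.** PSA every 4 weeks; progression at a rise of 10% or more; final slope from the last three PSAs.

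**Assumptions.** PSA noise SD 0.05–0.15 on the log scale; true PSADT 3–8 months; no drug effect; baseline slope b known. A man who has progressed at week 12 with a slope at or above b is stopped with probability f. Everyone else is read from weeks 16, 20 and 24. Benefit is taken as a lengthened PSADT.

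**Decision on the week 4–12 slope.** Squared deviations of 4, 8 and 12 from their mean sum to 32, so the slope has standard error SD/√32. Half of men lie above b, by 0.798 × SD/√32 on average. The mean excess is f × 0.5 × 0.798 × SD/√32. At SD 0.10 and f = 1 this is 0.0071 per week. At a 5-month PSADT, b = 0.693/21.74 weeks = 0.0319 per week, so the excess is 22%.

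**Decision on weeks 0–12.** An investigator may include C1D1. Squared deviations of 0, 4, 8 and 12 sum to 80, and the covariance of the two slopes is SD²/80, so √32 becomes √80: 0.5 × 0.798 × 0.10/8.944 = 0.0045, or 14%. With f = 0.5 it is 7%.

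**Sampling error for 34 men.** SD/(√32 × b × √34), before differences between men.

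| PSADT, noise | All stop, weeks 4–12 (simulated) | Half stop, weeks 0–12 (formula) | Sampling SE, 34 men |
|---|---|---|---|
| 3 months, 5% | 7% | 2.1% | 2.9% |
| 5 months, 10% | 22% | 7.0% | 9.5% |
| 8 months, 15% | 49% | 16.8% | 22.8% |

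In the last row the formula would give 53% for full stopping. The simulated 49% is lower because some men with steep slopes have not yet risen by 10%. If all stop on weeks 0–12, the range is 4% to about 34%. With stopping unrelated to PSA the excess is 0%. The fixed week 4–12 slope has a ratio of 1.00 throughout.

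**Mixed population.** Assume true PSADT of 2–12 months, a fitted baseline and the under-10-month entry filter, with the decision on weeks 4–12. The excess is 8–31% if all such men stop, 4–16% if half do and 2–8% if a quarter do. Applying the rule strictly at weeks 12, 24 and 36 gives 15–59%.

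**Early effect.** If 20% of men are flat from the start, the true mean slope ratio is 0.80. End-of-study PSADT reads 0.85–1.24 under full selective stopping; the fixed slope reads 0.80.

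**Other readings of the text.**
- End of Study PSA counted at week 16 (slope over weeks 8, 12 and 16): ratio 1.00 when the decision uses weeks 4–12. The noise in the two slopes, e16 − e8 and e12 − e4, is independent.
- Men stopped undosed on their C4D1 PSA treated as off before cycle 4, with no value: 1.00–1.01 under no effect. With 20% early responders it is 0.66–0.73 against a true 0.80, so the bias favours the drug.
- A decreased PSADT taken literally as the sign of benefit: 7–28% too flat.

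**The case against.** The strongest objection is that the stop rule above is not in the protocol. Section 6.7 requires no stop for PSA or PSADT, and PSADT appears only as an example of a reason to continue. This stands. The 7–49% range is what strict use of that example by every investigator would produce; it is not a forecast. With half of such men stopped on weeks 0–12, the bias is below one standard error for 34 men.

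Direction is also open. A reader might infer that end-of-study PSADT is biased against the drug as a matter of fact. The documents do not support that, because it depends on how 9.1 and the word decreased are read. The week-16 reading is the weaker one, for two reasons. Section 9.1's explanation for men off before cycle 4 holds only if the End of Study PSA is not counted. And a man stopped undosed at C4D1 had his last dose at about week 8, so his End of Study visit falls due by about week 12 (8 weeks plus 30 days). Section 9.1 does not settle whether such a man has a value at all.

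A reader might also infer that the trial's main conclusion is compromised. It is not: disease control is assessed at week 12 for everyone.

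Fixed-time PSA evidence does exist in part, through the 12-week primary endpoint and the 12-week percentage change in section 12.3. Neither is a PSADT, and the second serves only exploratory marker analyses.

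Finally, section 6.7 notes that PSA effects may take 12 weeks or more. A week 4–12 slope would miss those. This stands, and it is why the fixed slope should supplement end-of-study PSADT and not replace it.

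**Conclusion.** The point holds in a limited form. The measurement window for end-of-study PSADT can depend on the outcome, and no fixed-time PSADT is planned beside it. If men with steep slopes tend to be stopped, the summary leans toward apparent acceleration: about 2–17% if half of them stop on weeks 0–12, and 7–49% if all stop on the week 4–12 slope. These sizes rest on assumed PSA noise of 5–15%, an assumed stop rule and an assumed share stopped, none of which the documents give. The bias is nil if stopping is unrelated to PSA, and it may vanish or reverse under other readings. Because the endpoint is descriptive with no decision attached, this is a cheap, optional improvement of minor severity.

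**What to change.** In sections 2.2.2, 9.1 and 12.2.2, add the change from the pre-study ln(PSA) slope to the slope over C2D1, C3D1 and C4D1, for all treated men with these values, including men stopped at week 12. State that visits inside the ±3-day window satisfy the 8-week rule. Report this beside end-of-study PSADT, and split end-of-study PSADT by stop at week 12 versus later. Keep end-of-study PSADT. In 9.1, also say whether the End of Study PSA counts and whether a man stopped on his C4D1 PSA is off before cycle 4.

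The cost is one endpoint line, one definition and one table row, from PSAs already scheduled. Investigator discretion is unchanged. The added row covers only the first 12 weeks, misses later effects, and cannot by itself separate selective stopping from a delayed or waning effect. It also leaves in place the regression to the mean from the under-10-month entry filter, which affects both summaries.
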